The target population of the "Be Yourself" program are adolescents between 11 and 15 years old in secondary schools in Santa Catarina, Nuevo León. Eligibility criteria include being enrolled in a public school with access to a computer lab and internet, residing with your parents, and having become sexually active or not. The sample will be of 150 randomly selected participants. Participation will be assessed using a filter questionnaire, and adolescents will be required to register on the program's website throughout the intervention, with the option to withdraw at any time.

Sample size

To determine the sample size, the nQuery Advisor statistical package will be used. The aim is to have 150 participants, of which 75 will belong to the CG and 75 to the EG, applying a simple random probability sampling. The sample will be calculated with an error level of .05, a power of 90%, a moderate effect size of .3, considering a loss of 20%.

Design of the Intervention "Be yourself"

The "Be Yourself" educational intervention was designed to prevent sexual risk in high school adolescents through self-determined motivation. Based on MACSPEA, the model of stages of change and competency-based learning uses a website (https://www.s-t-mismo.com/) and a chatbot for monitoring and activities (Table 2). The intervention consists of three sessions that address the prevention of adolescent pregnancy and the strengthening of skills. It includes hands-on activities,

role-plays, and interactive sessions on contraceptive methods, effective communication, and informed decision-making. To do this, specialized human resources and specific materials are required for its execution. Manuals were designed for the intervention and training of the facilitator, and activity guides for adolescents^{21,14-18}.

		Thematic content	Time	Components of the intervention
		Pre-test assessment app	40 min	Access to the "Be Yourself" page
ų	1.	What is self-determined motivation?: Discovering our dreams	60 min	Personal factors
First Session	1.	My Body: Anatomy, Physiology, and Sexual Health.	60 min	 Age of onset of sexual life Pregnancy Prevention
	2.	Navigating relationships: preventing unplanned pregnancy in adolescents.	60 min	Knowledge
	3.	Exploring Goals and Values to Prevent Unintended Pregnancies	60 min	Contextual factors
Second Session	4.	Be yourself: stop, think and act; Introduction to Troubleshooting	60 min	1. Sexual communication with parents

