	5.	Role-play: open dialogue about sexuality	60 min	 Sexual communication with friends Sexual communication with a partner
uo	6.	Navigating the Sea of Healthy Choices: Exploring Our Motivation	60 min	Psychological factors
Third Session	7.	My Space, My Decisions Exploring Our Needs	60 min	 Intrinsic and extrinsic motivation Satisfaction and frustration:
Thir	8.	Negotiating Healthy Choices: Preventing Pregnancy and STIs	60 min	autonomy, relationships and skills
Keep	9.	Building Self-Determined Motivation in Teens: Strengthening Session on Website and Chatbot	Continued individual	 Self-determined motivation, Behavioral Intent and Sexual Prevention Behavior
		Post-test assessment app	40 min	Access to the "Be Yourself" page
		Total, hours	10 hours 20	minutes more

Description of the control treatment

For the GC, two theoretical sessions are planned. In the first, an orientation on sexual health for adolescents will be offered through a one-hour PowerPoint presentation. Topics of anatomy, physiology, biological changes in adolescence and contraceptive methods will be addressed, highlighting their appropriate use and the prevention of teenage pregnancy. In the second session, also one hour, sexual health self-care skills will be developed, discussing the importance of self-care, self-respect, and informed decision-making. There will be a Q&A session to address concerns and reflect on how self-care contributes to a healthy and safe sex life.

Control measures

Randomization of participants

Participants will be thoroughly selected to represent the EG. Software will perform a simple, blinded randomization, assigning participants to control or experimental groups. Managers will be informed about the "Be Yourself" sessions, the dates and locations of which will be published on the website and communicated verbally. The sessions will be group, with individual activities on the website and through a chatbot.

Recruitment

Recruitment for the intervention will take place in February 2025, after the authorization of the educational authorities. Adolescents from the educational institution will be openly invited and their suitability will be evaluated according to inclusion criteria. Those selected will be recorded and assigned to control and experimental groups using an ID to ensure data integrity.

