With informed consent, participants will access the website and the chatbot for information and registration. After accepting, they will answer filter questions and receive a detailed explanation of the process. Those who do not qualify will receive a transparent explanation.

On the website, participants will record their personal data for effective communication and reminders. They will be informed about the royalties of the program at the end of the project, motivating them to participate in all activities. The information will be stored securely for one year.

Measurements and data collection

Data collection for the study will include the use of a specifically designed Personal Data Card, which will collect information about the sexuality, marital status, and education of the participants. A variety of scales will be used to measure aspects related to adolescent sexual health and behavior. The Sexual and Reproductive Health Knowledge Scale, Cronbach's alpha between .77 and .81²¹, will assess knowledge in these areas, while the Sexual Issues Communication Instrument, Cronbach's alpha from .89 to .95, will analyze sexual communication between parents, friends, and partners²². The Aspirations Index, alpha greater than .78 and .94, will measure life goals, and the Basic Psychological Needs Satisfaction and Frustration Scale will have alphas of .90 and .86²³.

[figure not shown]
The Behavior Regulation Questionnaire, adapted to the Mexican context, will assess behavior regulation to prevent pregnancy, with alphas between .66 and .93²⁴. Likewise, the Sexual Activity Intention Scale and the Sexual Activity Scale will assess sexual intentions and behaviors, respectively, with alphas from .83 to .88 and .74 to .86²⁵. The Sexual and Reproductive Health

[figure not shown]
Practices Scale, which examines pregnancy prevention behavior, with alphas of .92, .77, .81 and .87 in its different adaptations²⁶.

The "Scale for the Assessment of Change on Sexual Behavior in Adolescents"27 will be adapted and validated, ensuring its reliability. To assess the acceptability and feasibility of the "Be Yourself" intervention, aspects such as participant satisfaction, meeting expectations, and facilitator quality will be analyzed, along with participant recruitment, screening, randomization, and retention procedures.

Participant Retention Plan and Follow-Up

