The retention plan for the "Be yourself" intervention includes the delivery of T-shirts and caps with the logo of the program at the end, weekly sessions to avoid information saturation and a three-month follow-up. Data collection will be done through the website using digital tools to assess the effectiveness and acceptability of the program. The fidelity of the intervention will be ensured by training the principal investigator in self-determination theory and developing supporting manuals and guides. Figure 1 presents diagram CONSORT²⁰, which details the eligibility criteria, intervention, and evaluation of sessions before, after, and during follow-up at three months.

Ethical considerations

This study complies with the ethical regulations of the Regulations of the General Health Law, ensuring respect for the dignity and rights of the participants. The protocol has been approved by the Ethics and Research Committee of the Faculty of Nursing of the Autonomous University of Nuevo León, with registration number FAEN-D-2021. Informed consent will be obtained from the parents and assent from the adolescents. Participation will be explained in detail to parents and teens, including risks and benefits. The research will be suspended if there is a risk to the health of the participants or if they wish to withdraw²⁸.

Data analysis plan

The research will use statistical software SPSS version 26.0 for data processing. The analysis will begin with the Kolmogorov-Smirnov test to evaluate the distribution of the data and determine the suitability of applying parametric or nonparametric tests. The statistical analysis will include a descriptive level, using percentages, means, and standard deviation, to assess feasibility and acceptability. For hypotheses, inferential tests such as paired sample t-test, ANOVA, and Mann-Whitney U will be used to examine knowledge about pregnancy prevention, sexual communication, motivation, satisfaction of psychological needs, sexual intention, pregnancy prevention behavior, and stages of change in sexual behavior²⁹.

Table 3 describes the objectives and hypotheses proposed in this study, both descriptive and inferential statistics will be used

Objective	Analysis	Statistical
1 Examining feasibility	Descriptive	Measures of frequency, central tendency, and dispersion: percentages, means, ranges, Standard Deviation, confidence intervals, recruitment and retention rates.

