2 Analyze acceptability	Descriptive	Percentages, means, ranges, Standard Deviation, confidence intervals, recruitment and retention rates
Hypothesis	Analysis	Statistical
 3 Hypothesized results: H 1. Knowledge about Pregnancy Prevention H 2. Sexual Communication Parent, Friends & Partner. H 3. Intrinsic and extrinsic motivation H 4. Satisfactory and Frustration of NPBs (autonomy, relationship and competencies) H 5. Self-Determined Motivation H 6. Intention in Sexual Activity H 7. Pregnancy Prevention Sexual Behavior H 8. Stages of Change for Sexual Behavior 	Inferential	t-test of paired or ANOVA samples Test de Friedman Test de Wilcoxon U de Mann-Whitney

Table 3. Statistical analysis by objective and/or hypothesis

EXPECTED RESULTS

The protocol of the "Be Yourself" intervention includes the structural design of the sessions, the development of two facilitator manuals and a participant workbook, and the creation of a web page with a chatbot based on OpenAI's GPT. The intervention is expected to increase adolescents' self-determination to abstain from sexual activity, improve their positive attitude toward sexuality, and expand their knowledge about pregnancy prevention. In addition, a greater adoption of preventive behaviors is anticipated compared to those who do not participate, which would suggest a positive impact on sexual decision-making.

FINANCING

This project did not receive any funding **DECLARATION OF CONFLICTS OF INTEREST** The author declares that they have no conflict of interest

REFERENCES

- World Health Organization (WHO)/PAHO. Syndromic management of sexually transmitted infections. 2022. ISBN 9789243593401. [Accessed July 19, 2024]. Available in: https://www.paho.org/es/temas/infecciones-transmision-sexual/manejo-sindromicoinfecciones-transmision-sexual
 - UNFPA. Systematization of scientific evidence on Comprehensive Sexuality Education. Updated version with new evidence about out-of-school HIE. UNFPA Regional Office for Latin America and the Caribbean, Panama. 2020. [Accessed July 19, 2024]. Available in: https://www.aprofaeduca.cl/wp-content/uploads/2021/08/Sistematizacio%CC%81n-deevidencias-cienti%CC%81ficas-sobre-la-Educacio%CC%81n-Integral-de-la-Sexualidad.pdf

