I	Problem	Self-determined motivati	on fo	r adolescent pregnanc	cy pre	evention.		
	Meta That adolescents achieve the stage of action and maintenance of self-determined motivation to prevent adolescent pregnancy.							
Ju	ıstificatio n					n for the Prevention of Pregnar e Competency-Based Learnin		
	As	ssumptions		Entrance Resources		Outputs Activities	Outputs	Results
a.	may not recog pregnancy if t	the precontemplation stage gnize themselves at risk for they lack awareness of the usequences and risks.		Human: Researcher, research assistant Financial:		Session 1: Getting to know yourself, steps to achieve your "Be Yourself" goals Knowledge and awareness	 "Be Yourself" faithfully implemented. Videos viewed on 	Primary 1.Increase in Self-Determined Motivation Indices to Prevent Adolescent Pregnancy (H5).
b.	If teens don't hat pregnancy pre	ave enough knowledge about evention, condom use, and they're likely to stay in the		Operating budget for the production of the material. Space: Computer		1. What is Self-Determined Motivation?: Discovering Our Dreams 2. My Body: Anatomy,	 web platform Participants discuss condom use and 	 2.Increased Level of Knowledge about Pregnancy Prevention (H1). 3.Improved Communication on Sexual Issues (H2.
c.	A lack of toward abstine	self-determined motivation ence and condom use can escents' transition to the		room of the educational institution Materials: didactic		Physiology and Sexual Health. Problem solving, negotiation.	negotiation 4. There is a discussion about abstinence and	 4. Change in Life Goals (H3): Significant increase in orientation toward intrinsic life goals (such as personal and academic development).
d.	A lack of se parents, friend difficult for te stage, where	exual communication with ds, and partners can make it evens to move into the action to they are expected to anges in sexual behavior and		and recreational materials for the intervention. Access to the web platform		3. Navigating Relationships: Preventing Unwanted Teen Pregnancy. Session 2: Building Personal Commitments: Conduct,	prevention of pregnancy 5. Negotiation and rejection skills are practiced	 5. Satisfaction of Basic Psychological Needs: autonomy, relationships and competence. (H4). Secondarys Intention to Risk and Protect (H6):

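### The outcome questionnaires are placed on the programme's own website, alongside the teaching material and chatbot, so the knowledge outcome (H1) is open to look-up and control pupils may be exposed to intervention content; the direction and size of any bias are uncertain

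*Protocol*

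**What the plan says.** Under Participant Retention Plan and Follow-Up, the protocol fixes where outcomes are collected: "Data collection will be done through the website using digital tools to assess the effectiveness and acceptability of the program". In Table 2, the pre-test and post-test rows each have 40 minutes and name the same component, "Access to the 'Be Yourself' page".

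The same site delivers the intervention. The Design of the Intervention section describes a website "and a chatbot for monitoring and activities". Item 9 of Table 2 is a "Strengthening Session on Website and Chatbot", to be used individually and without a fixed duration. Expected Results refers to "the creation of a web page with a chatbot based on OpenAI's GPT". The logic model lists videos viewed on the web platform among the outputs.

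On access, the Recruitment section says that consenting participants will use the website and chatbot for information and registration, and adds: "On the website, participants will record their personal data for effective communication and reminders". The eligibility section requires adolescents to register on the site. Neither statement is limited to one arm. The control treatment is two one-hour theoretical sessions, with no website teaching mentioned.

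The logic model lists "Increased Level of Knowledge about Pregnancy Prevention (H1") second under its Primary results, after self-determined motivation (H5).

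**The concern.** A knowledge test should measure what a pupil knows, under conditions that are the same in both arms. Here it is placed on the platform that holds the teaching material and a chatbot able to answer questions. Two things can follow.

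- **Look-up during the test.** A pupil can consult the content or the chatbot while answering. At analysis this cannot be told apart from learning. If it differs between arms after the programme, neither randomisation nor baseline adjustment removes it.
- **Control exposure.** Control pupils must enter the programme's site to be assessed. If teaching pages and chatbot are open to them, the control condition is no longer only the two theoretical sessions.

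At stake is the H1 comparison, one of the outcomes listed as primary in a pilot meant to judge preliminary efficacy. A false signal or a diluted one would mislead the decision about a larger trial.

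**Working it through.** **1. Are the assessments part of the programme timetable?** Table 2 has nine 60-minute topics and two 40-minute assessments: 9 × 60 + 2 × 40 = 620 minutes = 10 hours 20 minutes, which is the stated total. The pre-test and post-test are therefore timetabled with the programme. The 3-month measurement in Table 1 has no slot in Table 2, and its setting is not described.

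**2. Who can reach the content?** The text allows two readings.

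| Reading of site access | Support in the protocol | Consequence for H1 |
|---|---|---|
| Teaching content and chatbot used by the experimental group (EG) only | Individual website and chatbot activities are described with the 'Be Yourself' sessions; the control group (CG) has two theoretical sessions | Look-up mainly in the EG; contrast inflated |
| Site and chatbot open to all participants | The Recruitment and eligibility sections do not limit access by arm | Look-up possible in both arms, and control exposure; contrast nil, diluted or even reversed |

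Under either reading the H1 score may not be a closed-book score. Only the direction changes.

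**3. How large could it be?** The documents give no figure, so this is an illustration under assumptions. Let q_E and q_C be the shares of EG and CG pupils who look up answers, each gaining g SD, with the SD otherwise unchanged. The shift in the contrast is

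δ = (q_E − q_C) × g.

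Analysed numbers: 75 per arm less the planned 20% loss = 75 × 0.8 = 60. Test: two-sided two-sample t-test at .05, with no true effect. The non-centrality is δ × √(n/2), and √(60/2) = 5.48.

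| Assumption (g = 1 SD) | δ (SD) | Non-centrality, n = 60 | Chance of significance favouring EG, n = 60 | Same, n = 75 (no loss) |
|---|---|---|---|---|
| q_E = q_C | 0 | 0 | 2.5% | 2.5% |
| q_E − q_C = 10% | 0.1 | 0.55 | 7.8% | 8.8% |
| q_E − q_C = 20% | 0.2 | 1.10 | 19% | 23% |
| q_E − q_C = 30% | 0.3 | 1.64 | 37% | 45% |
| q_E − q_C = −10% | −0.1 | −0.55 | 0.6% | 0.5% |

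With less look-up and a smaller gain (5% of EG pupils, none in the CG, g = 0.5 SD), δ = 0.05 × 0.5 = 0.025 SD and the total two-sided error rate stays at about 5%.

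**4. Which outcomes are affected?** Look-up needs a correct answer to find. That applies to the knowledge scale. Communication, life goals, psychological needs, motivation (H5), intention and behaviour are self-reports without one.

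**The case against.** A reader might infer that only EG pupils can take the test open-book and that H1 is therefore biased in their favour. The documents do not support this. Website and chatbot access is given to participants of unspecified arm, and the EG's continued individual use makes greater familiarity plausible but no more.

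A reader might also infer that testing is unsupervised. The protocol does not say so. The tests have 40-minute timetabled slots, the school computer room and a research assistant are listed as resources, and a computer lab is an eligibility condition. This does not establish supervision, but open-book answering is a possibility and not a stated condition. Nor does anything place the 3-month test outside the school.

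Three further points are fair. Closing pages during a questionnaire is operational detail that might stand in the facilitator manuals, which are not shown. A pupil with internet access could look up answers elsewhere, so a lock on this site alone is not enough. No reward is tied to scores; the T-shirts and caps are for retention.

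A related inference is that replying on the programme's site, where personal data are recorded, pushes EG self-reports towards the taught answers. Personal data are recorded by participants generally, and an unbranded form would not undo the influence of the teaching itself, so this does not separate the arms on the documents' evidence.

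What remains is that the shared platform is a choice the protocol states, and the weakness exists under either reading of access.

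**Conclusion.** The point holds in a limited form. The protocol puts the outcome questionnaires on the site that holds the intervention, does not limit site and chatbot access by arm, and states no closed-book condition. H1 is therefore open to look-up, and the control arm to exposure.

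Direction and size are uncertain. The 0 to 0.3 SD range rests wholly on assumed look-up shares and an assumed 1 SD gain. Zero belongs in that range, and a negative value is possible. The 37% is the top of a chosen range and not an estimate. H5, the first-listed primary result, is not affected by look-up. The sample size does not change. This is a worthwhile, inexpensive improvement to make before recruitment, not a fault that invalidates the trial.

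**What to change.** Change the data-collection sentence under Participant Retention Plan and Follow-Up, and the two assessment cells of Table 2, to state that:

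- the pre-test, post-test and 3-month questionnaires are taken on a neutral form, separate from the programme pages and opened by study ID;
- programme content and chatbot are closed for that ID while the form is open;
- both arms are tested under the same conditions at all three time points, for example in a 40-minute slot in the school computer room already listed.

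In the Recruitment section, limit teaching content and chatbot to EG IDs, and leave registration open to both arms.

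Cost: one online form, an access setting by ID, and arranging the same test setting for both arms, including at 3 months. No extra pupils are needed. Questionnaire answers must be linked to website records by ID. Look-up outside the site is limited only by the common test conditions, so those should not be dropped in favour of the lock alone.

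### The hypotheses share one test list that does not tie the efficacy question to an EG-CG comparison and never uses the pre-test for adjustment

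*Protocol*

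**What the plan says.** The trial randomises adolescents to EG or CG and measures both before, at the end and at 3 months (Protocol, Studio Design, Table 1). Its stated aim is preliminary efficacy (Abstract; Introduction), and the Expected Results section anticipates more preventive behaviour than in non-participants. That is a question about the difference between arms.

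The Data analysis plan starts with a "Kolmogorov-Smirnov test to evaluate the distribution of the data and determine the suitability of applying parametric or nonparametric tests". It then says "inferential tests such as paired sample t-test, ANOVA, and Mann-Whitney U will be used to examine knowledge about pregnancy prevention" and the remaining outcomes. Table 3 puts all eight hypotheses, down to "H 8. Stages of Change for Sexual Behavior", in one row with one cell of tests: "t-test of paired or ANOVA samples Test de Friedman Test de Wilcoxon U de Mann-Whitney". No test is assigned to a hypothesis, a time point or a comparison of arms. ANCOVA, change scores, a group-by-time term and adjustment for the pre-test are not mentioned.

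**The concern.** A protocol may leave model detail to a statistical analysis plan. This one, however, chooses tests, gives a rule for selecting among them and maps them to hypotheses, and the mapping does not secure the comparison that randomisation was meant to deliver. On the parametric branch the named tests are paired t and ANOVA, so that branch contains an EG-CG comparison only if the ANOVA happens to include group.

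This matters because the control is active. In the two CG sessions, "contraceptive methods will be addressed, highlighting their appropriate use and the prevention of teenage pregnancy", and CG answers the same questionnaires at the same times. CG may improve as well. A significant before-after change in EG would then say little about the intervention, and a significant change in EG beside a non-significant one in CG would not show that the arms differ.

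The second loss is precision. The pre-test is collected from everyone, and the size and interval of the EG-CG difference are the main efficacy output of a pilot. The descriptive feasibility and acceptability objectives are not affected.

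**Working it through.** **What each listed test compares**

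| Test | Comparison |
|---|---|
| Paired t | within an arm |
| Friedman | within an arm, across time points |
| Wilcoxon | listed beside Friedman, so probably signed-rank (within an arm); the name alone could mean rank-sum |
| ANOVA | factors not stated: group, time, or group by time |
| Mann-Whitney U | EG against CG |

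**Inputs from the Protocol (Sample size).** Of 150 participants, "of which 75 will belong to the CG and 75 to the EG". Error level is .05, with "a power of 90%, a moderate effect size of .3, considering a loss of 20" per cent. Completers per arm: 75 × 0.8 = 60. Sidedness is not stated; two-sided is assumed.

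**The plan's own figure.** N = 150 can be reproduced in two ways:
- Two groups, .3 read as Cohen's f (d = 2f = 0.6): 59.4, so 60 per arm; 60/0.8 = 75 per arm, 150 in total.
- One group, paired test, .3 read as the standardised change dz: 118.7, so 119; 119/0.8 = 148.75, so 149.

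The sample size therefore does not settle which comparison was intended. Read as d between two arms, .3 needs 234 per arm before loss and does not reproduce 150.

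**Separate within-arm tests when the arms do not differ.** Assume independent participants and the same true gain dz in both arms. Let p be the power of a two-sided paired t-test with n = 60 (noncentral t, 59 df, noncentrality dz·√60). The chance that EG is significant and CG is not is p(1 − p).

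| dz (assumed) | p | p(1 − p) |
|---|---|---|
| 0.20 | .332 | .222 |
| 0.25 | .478 | .250 |
| 0.30 | .628 | .234 |
| 0.40 | .862 | .119 |
| 0.50 | .968 | .031 |

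The column p is the power to detect a real within-arm gain; it is not an error rate. The figure that bears on efficacy is p(1 − p), 3% to 25%. A direct two-sided 5% EG-CG test would favour EG wrongly in 2.5% of trials.

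**Precision from the pre-test.** Take d = 0.6, 60 per arm and pre-post correlation r (assumed; the Protocol gives none). ANCOVA multiplies the residual SD by √(1 − r²).
- Noncentrality: 0.6·√(60/2)/√(1 − r²) = 3.286/√(1 − r²).
- 95% CI half-width: 1.98·√(2/60)·√(1 − r²) = 0.361·√(1 − r²).

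| Analysis | Power | Half-width (SD) |
|---|---|---|
| Unadjusted | 90.3% | 0.36 |
| ANCOVA, r = .3 | 92.7% | 0.34 |
| ANCOVA, r = .5 | 96.4% | 0.31 |
| ANCOVA, r = .7 | 99.5% | 0.26 |

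If .3 means d = 0.3 instead, a normal approximation gives 37.6% unadjusted and 40.6/47.5/63.3% adjusted. The relative narrowing of the interval is the same.

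**The Kolmogorov-Smirnov step.** By simulation at d = 0.6, switching to ranks costs about 1 to 3 points: post-test t .903 against Mann-Whitney .893; change-score t .787/.903/.988 against Mann-Whitney on change .755/.886/.980 at r = .3/.5/.7. The Mann-Whitney runs used an assumed whole-number score from 0 to 20 with SD 3. The step does little harm by itself. It does lead to tests that, as listed, carry no pre-test adjustment.

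**The case against.** The strongest reply is that an EG-CG test is already planned. Mann-Whitney U appears in both places, the list in the text is open-ended, ANOVA could be a mixed group-by-time model, and the Expected Results section states a between-arm expectation. ANOVA factors and covariates are often left to a statistical analysis plan. An unadjusted comparison of randomised arms is valid, and at r = .3 the gain from adjustment is small (90% to 93% power).

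Much of this stands. A reader might infer that the trial has no between-arm test, or that the investigators will claim efficacy from before-after change in EG. The Protocol supports neither: the comparison is left open, not excluded, and nothing says how within-arm results will be read. Equal gains in both arms are also an assumption. They are plausible for knowledge, which CG is taught directly, and less so for self-determined motivation.

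What the reply does not remove is that the Protocol fixes one list for eight hypotheses without saying which entry answers the efficacy question, and makes no stated use of the pre-test for adjustment.

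**Conclusion.** The point holds as an improvement that costs no data. The test list should be tied to a pre-test-adjusted EG-CG difference. The 3% to 25% figure depends on assumed equal gains of 0.2 to 0.5 SD of change, independent participants, 60 completers per arm, and on someone reading separate within-arm tests as efficacy. The precision figures depend on an assumed correlation of .3 to .7, and the power figures also on reading .3 as d = 0.6.

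Three further inferences should not be drawn:
- N = 150 does not show that a between-arm test was intended, since a one-group paired test gives almost the same number.
- A group-by-time ANOVA is not the only form that would use the pre-test; a time-factor ANOVA or an ANOVA of change scores would too.
- The sentence "The sessions will be group, with individual activities on the website and through a chatbot" might suggest that clustering inflates the error here. The Protocol gives no group sizes or intraclass correlation, and that sentence follows the description of the Be Yourself sessions. It is a separate matter and does not support this point.

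**What to change.** In the Data analysis plan and Table 3:

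- For each scale score treated as continuous, make the inferential analysis the EG-CG difference with 95% CI, adjusted for that score's pre-test value, by ANCOVA at the end-of-intervention measurement. Give the same model at 3 months as a further analysis.
- For stages of change and other ordinal or frequency outcomes, use a between-arm model suited to the scale, adjusted for the baseline value. Identify outcomes by scale name, because the logic model numbers its hypotheses up to H9 and Table 3 stops at H8.
- Do not let the Kolmogorov-Smirnov result replace this analysis. Report rank-based results as sensitivity analysis.
- Label paired t, Wilcoxon and Friedman results as descriptive.

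The cost is a rewritten paragraph, a revised Table 3 and a little analysis work in the SPSS software already named. No new data, visits or participants are needed.

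### The tests named in Table 3 use only pupils measured at every occasion each test needs, so loss related to outcome in different ways by arm can bias the comparison of arms

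*Protocol*

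**What the plan says.** - **Occasions.** Table 1 shows three measurements in each arm: before, at the end and at 3 months. The section on participant retention and follow-up repeats this: "evaluation of sessions before, after, and during follow-up at three months".
- **Expected loss.** The sample size section states "The aim is to have 150 participants, of which 75 will belong to the CG and 75 to the EG", "considering a loss of 20" per cent. The figure is not split by arm or by occasion.
- **Tests.** Table 3 lists for H1 to H8: "t-test of paired or ANOVA samples Test de Friedman Test de Wilcoxon U de Mann-Whitney". The data analysis plan says in prose that "inferential tests such as paired sample t-test, ANOVA, and Mann-Whitney U will be used", after a Kolmogorov-Smirnov check of the distribution.
- **Load.** Table 2 gives the experimental group (EG) nine 60-minute units, continued individual website and chatbot work, and two 40-minute assessments, 10 h 20 min in total. For the control group (CG): "For the GC, two theoretical sessions are planned", each of one hour.
- **Retention.** Retention rates appear in Table 3 only as descriptive measures for feasibility and acceptability.

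**The concern.** The protocol expects to lose one pupil in five and names no inferential method that can use a partly complete record. A pupil with scores before and at the end but none at 3 months is deleted from a Friedman test or a classical repeated-measures ANOVA over the three occasions. The end score, which shows how that pupil stood before leaving, is then lost too.

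Completers are not the randomised groups. If pupils doing poorly leave the long programme while loss from the short one is unrelated to results, the experimental mean rises with no effect of the programme. The aim is preliminary efficacy, and an estimate inflated in this way would be carried into the planning of a later trial.

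**Working it through.** **1. What each named test needs**

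| Test | Pupils used | Compares arms? |
|---|---|---|
| Friedman | all three occasions present | no, within group |
| ANOVA, if classical repeated-measures | all three present | only with a group factor |
| Paired t, Wilcoxon (signed-rank) | both occasions of the pair present | no, within group |
| Mann-Whitney U | measured at the occasion compared | yes |

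A pupil missing only the 3-month score therefore stays in a before/end paired test and in Mann-Whitney U at the end. Bias between arms can enter through ANOVA with a group factor and through Mann-Whitney U.

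**2. The plan's own sample size**

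Inputs (sample size section): alpha .05 (two-sided assumed), power 90%, effect size .3, loss 20%. The metric of .3 is not stated. Read as Cohen's f it equals d = 0.6. Then n per arm = 2(1.960 + 1.282)²/0.6² = 58.4, so 59. The t-based value is 59.35, so 60, and 60/0.8 = 75 per arm, which is the stated figure. With 60 per arm, power at d = 0.6 is 0.90, so the allowance covers the planned loss under this reading.

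**3. Precision**

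If all loss falls at 3 months, deletion over all three occasions cuts the end comparison from 75 to 60 per arm. The standard error rises by √(75/60) = 1.118, and power at d = 0.5 falls from 0.86 to 0.78. This does not apply to Mann-Whitney U at the end or to a before/end pair.

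**4. Bias, main scenario (all inputs below are assumptions)**

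True difference 0.60 SD. Correlations: before-end .5, end-3 months .6, before-3 months .5. EG pupils leave before 3 months with log-odds falling by 1.2 per SD of the end score; CG pupils leave at random.

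By simulation, EG completers' mean end score lies above that of the whole EG by 0.20 SD at 20%/20% loss (EG/CG) and 0.29 SD at 30%/10%. The rest follows nearly by hand:

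- 3-month difference: .6 × 0.20 = 0.12 and .6 × 0.29 = 0.17. Simulated completers give 0.72 and 0.77 to 0.78 against the true 0.60.
- 3-month change from baseline: (.6 − .5) × 0.20 = 0.02 and (.6 − .5) × 0.29 = 0.03.
- Before-to-end change, if pupils without a 3-month score are deleted: (1 − .5) × 0.20 = 0.10 and (1 − .5) × 0.29 = 0.15.
- Regression of the 3-month score on the observed earlier scores within each arm, averaged over all pupils: 0.60 and 0.60 to 0.61.

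**5. Bias under other mechanisms (assumed: no true effect, all correlations .6, slope 0.5 to 1 per SD)**

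False EG−CG difference in SD:

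| Loss depends on | EG/CG loss | 3-month score, completers | 3-month change, completers | 3-month score, all observed data used |
|---|---|---|---|---|
| end score, EG only | 20%/20% | 0.06 to 0.10 | about 0 | about 0 |
| end score, EG only | 30%/10% | 0.09 to 0.16 | about 0 | about 0 |
| unseen 3-month score, EG only | 20%/20% | 0.10 to 0.18 | 0.04 to 0.07 | 0.06 to 0.10 |
| unseen 3-month score, EG only | 30%/10% | 0.14 to 0.25 | 0.06 to 0.10 | 0.08 to 0.15 |
| unseen 3-month score, both arms | 20%/20% | about 0 | about 0 | about 0 |
| unseen 3-month score, both arms | 30%/10% | 0.09 to 0.16 | 0.03 to 0.07 | 0.05 to 0.10 |
| nothing (random) | either | about 0 | about 0 | about 0 |

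**The case against.** The strongest reply is that analysis sets and missing-data rules commonly sit in a statistical analysis plan, which is not shown, so silence on them is no error. A reader might infer that the protocol prescribes a completers-only efficacy analysis. It does not. The prose list is open, ANOVA is not called repeated-measures, and nothing rules out imputation before the tests. That part of the reply stands. What remains is that Table 3 does name methods for H1 to H8, and none of them, applied as listed, keeps a pupil who lacks an occasion the test needs.

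Two further inferences are tempting and also fail. One is that every named test drops anyone with any missing occasion; the first table in the working shows otherwise. The other is that the planned loss leaves the trial short of power; at d = 0.6 it does not.

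It is also fair to say that unequal, outcome-related loss is assumed. The protocol gives one overall figure, and the difference in load makes such loss plausible without showing it. Finally, this is a pilot with a retention plan that reports its retention rates. That helps to detect unequal loss but does not correct for it.

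**Conclusion.** The point holds as a conditional one. The named tests are complete-case for the occasions they use, and between-arm results from ANOVA or Mann-Whitney U can be biased if loss is related to outcome differently by arm. Under the main assumed mechanism the 3-month difference is too large by about 0.12 to 0.18 SD, or 20% to 30% of a true 0.60 SD. The 3-month change-from-baseline contrast is off by only 0.02 to 0.03 SD there, and by up to 0.10 SD in the scenarios with loss driven by unseen scores. Bias is near 0 when loss is unrelated to outcome, or has the same mechanism and rate in both arms.

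Bias, not power, is the main issue. That rests on reading .3 as Cohen's f, which the protocol does not state. The change is worth making because it is cheap, but the protocol does not show that the bias will occur.

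**What to change.** For the scale scores, replace the repeated-occasion tests in Table 3 with one linear mixed model: arm, occasion and arm × occasion, with unstructured covariance across the three occasions. Include every randomised pupil in the assigned arm with all available occasions. Report the EG−CG difference at the end and at 3 months, each with a 95% confidence interval. Keep the completer tests as a sensitivity analysis.

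The cost is a change of wording in the data analysis plan and Table 3 and slightly more programming. The named software fits this model, and no new data or pupils are needed. The model relies on data missing at random given the observed scores. If loss depends on unseen scores, bias is reduced but not removed: 0.05 to 0.15 SD remained in the scenarios above where such loss biased the completers.
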